²An intervention is defined as a manipulation of the subject or subject’s environment for the purpose of modifying one or more health-related biomedical or behavioral processes and/or endpoints. Examples include: drugs/small molecules/compounds; biologics; devices; procedures (e.g., surgical techniques); delivery systems (e.g., telemedicine, face-to-face interviews); strategies to change health-related behavior (e.g., diet, cognitive/behavioral therapy, exercise, development of new habits); treatment strategies; prevention strategies; and, diagnostic strategies.

³ 3. Health-related biomedical or behavioral outcome is defined as the pre-specified goal(s) or condition(s) that reflect the effect of one or more interventions on human subjects’ biomedical or behavioral status or quality of life. Examples include: positive or negative changes to physiological or biological parameters (e.g., improvement of lung capacity, gene expression); positive or negative changes to psychological or neurodevelopmental parameters (e.g., mood management intervention for smokers; reading comprehension and /or information retention, behavioral intervention for psychiatric symptoms); positive or negative changes to disease processes; positive or negative changes to health-related behaviors; and, positive or negative changes to quality of life.

similar designs and our own trials, we expect a common within-group standard deviation of 5kg and a 20% attrition rate. [10-12] Hypothesis testing will be based on linear mixed effects models for longitudinal data, which increase power by fully exploiting the strong correlation in weight measures across time. Given these assumptions, if a total of N=160 participants (BE mHealth: N=80; mHealth: N=80) are enrolled, the trial will have 88% power to detect a statistically significant result. Accounting for attrition, 35 more participants will be added, so a total of 195 participants will be needed for this trial.

For EACH Participant Population Describe Screening Procedures, if applicable:

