BE mHealth overview. Tailored evidence-based obesity treatment content may be necessary but not sufficient for adults from economically disadvantaged backgrounds. Newly identified behavioral and cognitive processes – lack of reinforcement and bias for the present – if addressed, may optimize treatment success in this underserved population. Thus, behavioral economics strategies designed to target lack of reinforcement and bias for the present will be included in this arm. Specifically, the proposed behavioral economics intervention will include the mHealth, tailored intervention (described above); small monetary reinforcers to immediately engage participants in treatment and promote initial weight loss; and Episodic Future Thinking to address bias for the present and promote longer-term weight loss success. BE mHealth intervention details are provided below. All proposed behavioral economics treatment content and contact schedules are based on our previous, successful approaches.

BE mHealth strategies. In addition to the online mHealth tailored intervention described above, the BE mHealth intervention platform will include two behavioral economics intervention strategies: a reinforcement paradigm and Episodic Future Thinking. These intervention strategies will target lack of reinforcement and bias for the present. Given strong evidence that monetary reinforcers promote treatment engagement, small financial reinforcers will be used immediately at treatment start. However, such reinforcers cannot be delivered indefinitely. Thus, as weight loss occurs, which naturally provides its own reinforcement (e.g., improved mood, energy, appearance, health),^[39-42] monetary reinforcement will taper. EFT training will begin at week 8. The 8-week time point was chosen by examining the weight loss trajectories in our pilot, as suggested by a previous reviewer. Indeed, there was a reduction in magnitude of weight loss with financial reinforcement alone at month two (month 1: -3.6kg; month 2: -1.8kg; month 3: -1.3kg). Thus, EFT will be added at this time to promote additional and sustained weight loss. Taken together, we believe this scaffolding approach that first provides financial reinforcement and then transitions to longer-term sustainable weight management strategies (EFT) is most beneficial. Detailed information on reinforcement delivery and EFT is provided below.

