Reinforcement. Small financial reinforcers will be delivered consistent with our previous, successful paradigms in this population. During the first three months of treatment, participants will receive reinforcement each week, which will then taper to every other week, once a month, and eventually end (see figure above). During reinforcement weeks, small financial reinforcers will be delivered contingent

upon behavior change and weight loss. Specifically, each week participants self-monitor at least 5 days of weight, diet, and activity, they will receive a monetary reinforcer, which will range anywhere from \$1 to \$10 (e.g., Week 1: \$10, Week 9: \$2). The maximum amount of monetary reinforcement to be earned for self-monitoring behavior will be a total of \$65 for the entire 12-month program. Participants will also complete an objective virtual weigh-in at months 3 and 6. Those who lose 5-10% of initial body weight will receive \$50 and those who lose $\geq 10\%$ will receive \$100 at their weigh-in visit. Self-monitoring banks will also be ‘paid-out’ at these visits. As participants are developing success experiences with weight loss, which naturally provides its own reinforcement,^[39-42] monetary reinforcers will taper and eventually end. During this time period, training in Episodic Future Thinking will begin.

Episodic Future Thinking (EFT). EFT will begin at week 8. EFT involves the production of positive, vivid, meaningful future events (e.g., church get-together, family gathering, wedding) for which the behavioral goal (weight loss) is important; vivid imagination of events is created through integration of basic cognitive systems (narrative, emotional, sensory, and spatial).^[37, 69] These vividly imagined events are then distilled into brief cues that conjure the event. Cues can take the form of approximately a few sentences that capture the event, pictures that embody the event, or brief audio recordings of the event.^[37, 38] Participants are then exposed to these cues on a daily basis via our mHealth platform.

Component unique to the mHealth only treatment arm.

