The primary outcome for which the trial is powered is weight change from baseline to month 12. Differences in baseline characteristics in BE mHealth vs. mHealth participants will be examined using either t-test, Chi-Square tests or analysis of variance when appropriate. If baseline differences exist, they will be controlled for in outcome analyses. Distributional properties of continuously scaled variables will be examined to determine if normalizing transformations should be applied or if distributions other than normal should be used in the models. Pairwise contrasts among study groups using linear mixed effects models will be fitted by restricted maximum likelihood using REML as implemented in the PROC MIXED procedure or PROC GLIMMIX SAS 9.3 if residuals do not meet normality. Unconditional models will be fitted to assess for variability in participant intercepts and slopes, and determine whether these factors should be treated as random effects in conditional models. Unconditional models will also be used to evaluate whether the trajectory of the outcome is best characterized as linear / non-linear (quadratic and cubic). Estimated mean differences will be developed using linear contrasts and assessed with Wald statistics. These analyses will result in a detailed model of weight change across the 12-month trial. Within the linear mixed effects model, an a priori test of the difference between least squared means for treatment arms at the 12-month time point, adjusted for covariates, will test for between-arm differences at the 12-month assessment.

Missing data. Although concerted effort will be made to minimize missing data, we anticipate missing data due to refuted responses or lost to follow-up. Type of missingness will be evaluated and missing values will be imputed using full information or restricted maximum likelihood estimation^[100] depending on type of missing data, completely at random or just random missing data. All variables in our models will be used to impute missing data. Sensitivity analyses will be used to compare results with and without imputed values.

Inclusion/Exclusion Criteria:

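### The month-12 primary test depends on a time curve picked from pooled data and on baseline adjustment only if a difference is seen; the cost runs from nil upward by reading, and fixing the model is nearly free

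*Combined protocol and SAP*

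**What the plan says.** The Data Analysis section names the outcome: "The primary outcome for which the trial is powered is weight change from baseline to month 12". The Design overview and Assessments sections also call it weight change. The powered test is "an a priori test of the difference between least squared means for treatment arms at the 12-month time point", taken within a linear mixed model fitted by REML and adjusted for covariates that are not listed.

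Two features of that model are left to the data. Unconditional models are used to "evaluate whether the trajectory of the outcome is best characterized as linear / non-linear (quadratic and cubic", with no selection rule. For baseline variables the rule is: "If baseline differences exist, they will be controlled for in outcome analyses".

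The dependent variable of the mixed model is not written. The Justification of Sample Size section says such models "increase power by fully exploiting the strong correlation in weight measures across time", which points to repeated weights. The same section gives the planning SD: "we expect a common within-group standard deviation of 5kg and a 20% attrition rate". Assessments fall at baseline and months 2, 6 and 12, with a further 18-month visit for three of the four cohorts.

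**The concern.** The pooled trajectory shows how the average participant loses weight. It does not show how the gap between arms develops, and the gap is what the test measures. A curve that fits the pooled data well can still be too stiff for the gap at month 12.

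The baseline rule has a similar weakness. Baseline weight is probably the strongest predictor of later weight, whether or not the arms happen to differ on it. Tying its inclusion to observed imbalance leaves precision to chance.

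The wording does not settle the response. Weight change suggests change scores. A cubic needs four occasions, however, and within 12 months that means baseline is one of the modelled rows. The same data could therefore give different primary estimates under choices the text allows. At stake are the size of the month-12 estimate and the power of the only powered comparison.

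**Working it through.** **Inputs from the protocol.** Target difference 2.5 kg, SD 5 kg, 80 per arm, 20% attrition, 195 randomised 1:1, 5% type I error, visits at 0, 2, 6 and 12 months. After attrition, 195 × 0.8 / 2 = 78 per arm.

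**Assumed, because the protocol gives none.** The shape of the arm gap over time; weight SD 15-25 kg (random-intercept SD); random-slope SD 0.367 kg/month and residual SD 1.67 kg. The last two are set to give the planned change SD: 144 × 0.367² + 2 × 1.67² = 19.40 + 5.58 = 24.97, SD 5.0.

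**1. The plan's own figure.** SE = 5 × √(2/80) = 0.791, and 2.5/0.791 = 3.16. Power = Φ(3.16 − 1.96) = 88.5%, or 88.2% by the noncentral t, two-sided. The stated 88% is reproduced as a test of 12-month change. At 78 per arm, SE = 5 × √(2/78) = 0.80 and power is about 88%.

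**2. Change scores at months 2, 6 and 12.** With three occasions, both categorical visit and a quadratic are saturated. The estimate is −2.50 kg and power about 88%, so there is no bias and no loss. A cubic fully crossed with arm on four occasions gives the same.

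**3. Baseline as a response row, quadratic crossed with arm, baseline-to-12 contrast.** At times 0, 2, 6 and 12, the one pattern a quadratic cannot fit has weights (−5, 9, −5, 1), with sum of squares 132. Random intercept and slope lie within the quadratic, so the fitted gap is the least-squares one. With a zero gap at baseline:

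estimate = g12 − (6/132)(9·g2 − 5·g6 + g12) = g12 − (9·g2 − 5·g6 + g12)/22

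The variance of the contrast per person is 19.40 + (2 − 36/132) × 1.67² = 24.21, so SE = 4.92 × √(2/78) = 0.788.

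| Assumed gap at months 2 / 6 / 12 (kg) | Estimate (kg) | Power |
|---|---|---|
| −0.8 / −1.8 / −2.5 (gradual) | −2.5 + 0.7/22 = −2.47 | 88% |
| −1.5 / −2.5 / −2.5 | −2.5 + 3.5/22 = −2.34 | 84% |
| −2 / −2.5 / −2.5 | −2.5 + 8/22 = −2.14 | 77% |
| −2.5 / −2.5 / −2.5 (extreme) | −2.5 + 12.5/22 = −1.93 | 69% |

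Constraining the arms to a common baseline gives the same result for the extreme gap (−1.93 kg, 69%).

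How often a quadratic would be chosen cannot be said from the protocol. In simulations with three assumed BE mHealth trajectories and an assumed |z| > 1.96 rule, the cubic was chosen in 99%, 41% and 6% of runs under the extreme gap.

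**4. Raw weight at month 12, baseline weight not in the model.** At intercept SD 20, the month-12 variance is 400 + 19.40 + 1.67² = 422.2, so SE = 20.55 × √(2/78) = 3.29 kg against 0.80 kg, and power is about 12%. At SD 15 it is 17% and at SD 25 it is 9%. Curve choice hardly matters here: for the extreme gap the quadratic gives −2.5 + 12.5/132 = −2.41 kg.

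**5. Does the conditional rule rescue reading 4?** If the trigger is p < 0.05 (assumed), it fires in about 5% of randomised trials. Simulated power is then 19%, 13.5% and 11% at SD 15, 20 and 25. At SD 20, the largest imbalance that would not trigger it is 1.96 × 20 × √(2/97.5) = 5.6 kg, over twice the target effect.

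**6. Type I error.** Choosing the curve without the arm term does not by itself inflate it. Under reading 4 with the conditional rule, null rejection was 1.2-1.7%, which is conservative.

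**The case against.** The strongest reply is that the response is clear enough. Weight change is named in three sections, and the Data Analysis text describes the result as a model of weight change just before it states the test. The 5 kg SD and the 88% make sense only for change. On that reading the cost is nil. This largely stands. A reader might infer from step 4 that the trial is set to lose most of its planned power. The documents do not support that, because the loss belongs to a raw-weight, unadjusted reading that their own wording makes less likely.

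The 69% figure is also open to challenge. It needs the whole gap by month 2 and none added later. Incentives are indeed front-loaded, since "participants will receive reinforcement each week, which will then taper to every other week, once a month, and eventually end" after the first three months. But Episodic Future Thinking starts at week 8, and "EFT will be added at this time to promote additional and sustained weight loss". If it works as intended, the gap keeps growing, which is the mild case. The plan also allows a cubic, which removes the bias if crossed with arm.

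Three smaller points stand. A month-12 arm contrast implies an arm-by-time term even though none is written. The gap shapes, weight SD and trigger level are assumptions. And data-driven modelling might suggest more false positives, but neither mechanism produces them here.

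The two rules themselves remain. Baseline adjustment is conditional on observed imbalance, and the curve is chosen from pooled data. Limits of Assumptions, under Stopping Rules, calls baseline differences large enough to threaten validity exceedingly unlikely, so the adjustment rule should seldom be expected to act.

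**Conclusion.** The point holds as a weakness in the specification of the primary analysis. It does not show that the trial is underpowered.

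- **Change scores with saturated time:** no bias, about 88% power.
- **Baseline as a response row with a quadratic:** understatement of 0.16 to 0.36 kg and power 84-77% for moderately front-loaded gaps; 69% in the extreme case; no material loss for a gradual gap.
- **Raw month-12 weight without baseline weight, a less likely reading:** about 9-17% power, rarely rescued by the conditional rule.

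The step 3 estimates depend only on the assumed gap shape. The power figures also rest on 78 per arm and a change SD of 5 kg, and the last range on an assumed weight SD of 25 to 15 kg. The matter should be fixed because both choices are otherwise settled after pooled curves and baseline tests have been seen, and the better rule costs almost nothing.

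**What to change.** Write the primary model into the Data Analysis section:

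- **Response:** weight change in kg from baseline at months 2, 6 and 12.
- **Fixed effects:** arm, visit as a categorical factor, arm by visit, baseline weight always included whatever imbalance is observed, and the randomisation factors: race/ethnicity, sex and cohort (blocks are permuted within cohort).
- **Primary test:** the arm difference at month 12, fitted by REML.

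Drop the baseline-difference trigger for the primary analysis. Keep the polynomial growth curves as secondary, descriptive analyses. An unstructured within-person covariance is a reasonable default, though the point does not depend on it.

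The cost is wording and a few extra parameters. SE is about 0.80 kg against 0.79 kg for a quadratic, and the target effect, SD, N and planned power are unchanged. The document is dated December 2025, cohort 1 recruitment was expected in summer 2021, and the text does not say whether the arms have been compared. If any arm comparison has already been made, label the change as post hoc.

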Design overview. This study will examine the efficacy of a mHealth Behavioral Economics weight loss treatment for adults from economically disadvantaged backgrounds. Participants will be randomly assigned to either the Behavioral Economics mHealth intervention (BE mHealth) or mHealth only (no behavioral economics treatment components). Both interventions will: (a) include behavioral weight loss material tailored to this population, (b) be matched for interventionist contact, and (c) be 12 months in duration. The only difference between the two arms is the inclusion of behavioral economics strategies in BE mHealth. Specifically, BE mHealth will involve provision of reinforcers (small monetary reinforcers) and training in Episodic Future Thinking (see below for details). Assessments will occur at baseline, 2, 6, and 12 months (primary endpoint) and at the 18-month follow-up (C1-C3). The 18-month follow-up is included to explore whether participants continue to engage with the two interventions and the durability of treatment effects in the two arms. The primary outcome for which the trial is powered is weight change at month 12. Mediators (reinforcing value of food, delay discounting), moderators (e.g., stress, resilience, environment), and cost-effectiveness of the two interventions will also be explored. Visits (orientation / consent, assessments, and intervention) will be conducted via a video conferencing platform like Zoom.

Randomization. Eligible participants will be randomized to either BE mHealth or mHealth. The statistician will conduct the randomization and will use a permuted block randomization scheme for each cohort. Given evidence of differential weight loss by racial / ethnic background and sex^[40, 64] randomization will be stratified on these variables. A 1:1 randomization scheme will be used.

Overview of the two interventions. The two interventions are matched on treatment modality, participant contact, treatment duration, and tailored weight loss content. That is, the only way in which BE mHealth and mHealth differ is in behavioral economics strategies. Please see table and details below.

Similarities between BE mHealth and mHealth. The two interventions will be matched on treatment modality (primarily mHealth), contact (a total of 16 sessions),

Similarities		
mHealth treatment platform	✓	✓
Tailored behavioral weight loss treatment materials	✓	✓
Up to 16 sessions	✓	✓
12-months of treatment	✓	✓
Differences		

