Healthy Thinking. To control for contact associated with EFT sessions and daily cue delivery in BE mHealth, mHealth only will include Healthy Thinking cues. Healthy Thinking cues have been used as a successful control in our EFT studies.^[38] To control for the BE mHealth contact schedule, at months 1, 2, 3, 6, and 9, mHealth only participants will also attend individual virtual sessions. During these sessions, participants will be given a list of Healthy Thinking educational cues (e.g., decrease snack intake) and choose which cues they wish to receive on a daily basis via the app.

Assessments. Assessments will occur virtually. Primary outcome is weight change during the 12-month treatment. Demographics will be collected at baseline.

Demographics. Gender, age, race, ethnicity, education, income, and household size will be collected.

Weight. Weight will be collected using a bathroom digital scale, or via an e-scale that securely transmits participant weights back to study staff via cell tower. To ensure gold-standard research-based weigh-in procedures are used, under such circumstances, participants will complete this remote weigh-in via Zoom. During the virtual meeting, research staff will provide the participant with detailed weigh-in instructions (place scale on hard surfaced floor, one layer of clothing, no shoes or heavy jewelry, empty pockets, etc.). Weight will then either be remotely transmitted (in the use of e-scales) or participants will show research staff their weight (in the use of regular digital bathroom scales). Height will be assessed via self-report. No other physical measures are included.

Adverse Event Interviews. The occurrence of adverse events will be assessed via Qualtrics, email or phone instead of in person.

Quality control.

Data management. Survey data will be collected using Qualtrics (see Human Subjects for security details). Forty-eight hours prior to their visit, participants will receive a link to complete their measures. On the day of the visit, the assessor will log on and review participant responses for completion; missing data will be addressed during the visit. The assessor will record all physical measurements in Qualtrics or via standardized form. Any data not captured electronically (e.g., Qualtrics form) will be entered into a password protected data entry and storage system, which provides programmatic protection against

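### The primary month-12 test has no fixed covariates: baseline variables enter only if they are found to differ between arms, so baseline weight and the stratification factors should be pre-specified

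*Combined protocol and SAP*

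**What the plan says.** The outcome is named three times, each time as change. Data Analysis opens with "The primary outcome for which the trial is powered is weight change from baseline to month 12", the design overview has "The primary outcome for which the trial is powered is weight change at month 12", and Assessments has "Primary outcome is weight change during the 12-month treatment".

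The test is described in Data Analysis. A linear mixed effects model is fitted, and "Estimated mean differences will be developed using linear contrasts and assessed with Wald statistics". The primary comparison is "an a priori test of the difference between least squared means for treatment arms at the 12-month time point, adjusted for covariates". That sentence does not list the covariates. It also does not say whether baseline is subtracted, used as a covariate, or kept as the first repeated measure.

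The one rule on covariates is in the same section. Arms are compared on baseline characteristics by t-test, chi-square or analysis of variance, and "If baseline differences exist, they will be controlled for in outcome analyses". No variables and no threshold are given.

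Under Randomization, race/ethnicity and sex are singled out because weight loss is thought to differ by them, and "randomization will be stratified on these variables". They are not named as model covariates.

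The Justification of Sample Size assumes a 2.5 kg difference, a "common within-group standard deviation of 5kg and a 20% attrition rate", and 80 per arm, and states 88% power. It adds 35 participants for attrition, giving 195.

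**The concern.** In a randomized trial, testing for baseline differences is a poor guide to which covariates belong in the model. Any imbalance is due to chance. What makes a covariate worth including is its relation to the outcome, and that is known beforehand. Baseline weight is the obvious candidate, and the plan itself regards race/ethnicity and sex as related to weight loss. Under the stated rule all three may be left out, and the choice is made after the data have been examined with no threshold to bind it.

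Two things are at stake. One is pre-specification: several different primary models fit the same text. The other is precision, and how much depends on how baseline enters. If the response is change, baseline is already removed by subtraction and an extra baseline term matters little. If raw month-12 weight were compared with no baseline term, the comparison would carry the full spread of body weight between people.

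**Working it through.** **Inputs from the documents.** Difference 2.5 kg, SD 5 kg, 20% attrition, 80 per arm and 195 in total (Justification of Sample Size); 1:1 allocation (Randomization); 5% Type I error (Stopping Rules, Limits of Assumptions). A two-sided test is assumed because it reproduces the stated power.

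**1. The plan's own figure.** SE = SD × √(2/n), with power from the noncentral t distribution.
- 80 per arm: SE = 5 × √(2/80) = 0.791 kg, power 88.2%. The stated 88% reproduces.
- 195 less 20%: 195 × 0.8 = 156, or 78 per arm. SE = 5 × √(2/78) = 0.801 kg, power 87.3%.

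The 5 kg can only be an SD of change. BMI 25 to 55 at an assumed height of 1.65 m spans about 68 to 150 kg (25 × 1.65² and 55 × 1.65²), far too wide for a raw-weight SD of 5 kg.

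**2. Change as response, baseline weight always included.** Residual SD = 5 × √(1 − r²), where r is the correlation between baseline weight and change. The documents give no r, so a range is assumed. The SEs include a small allowance for estimating the extra term (78 per arm).

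| Size of r | SE (kg) | Power |
|---|---|---|
| 0 | 0.803 | 87.1% |
| 0.1 | 0.799 | 87.5% |
| 0.2 | 0.787 | 88.4% |
| 0.3 | 0.766 | 90.0% |

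Against 87.3% this is −0.2 to +2.7 points.

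**3. Weight at 0, 2, 6 and 12 months, baseline means constrained equal.** For completers, assuming a random-intercept SD of 12 to 22 kg, a random slope, a residual SD of 1 to 2 kg, an SD of 12-month change of 5 kg and an intercept-slope correlation of 0 or −0.2, the SE is 0.779 to 0.801 kg and power 87.3% to 89.0%.

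**4. The conditional rule applied to change.** Simulation (20,000 trials for power, 40,000 under the null), adjusting for baseline weight only when its baseline test is significant: power 87.3% to 87.7%, Type I error 4.8% to 5.0%, mean estimate about −2.5 kg. The rule does almost nothing to the operating characteristics and introduces no bias.

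**5. The remote case: raw month-12 weight, no baseline term.** The raw-weight SD is not in the documents; 12 to 22 kg is assumed. At 12 kg, SE = 12 × √(2/78) = 1.92 kg and power 25%; at 22 kg, SE = 3.52 kg and power 11%. With an assumed p<0.05 trigger the conditional rule adjusts in about 5% of trials, and power is still only 27% to 12%. Putting baseline weight in as a covariate removes the loss. With equal SDs s at both times and an SD of change of 5 kg, the correlation is ρ = 1 − 25/(2s²) and the residual SD is s√(1 − ρ²): 4.89 kg at s = 12 and 4.97 kg at s = 22, giving about 88% power.

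**The case against.** The strongest reply is that the section, read as a whole, already answers most of this. It opens with change from baseline, describes the fitted model as one of weight change, and provides for linear contrasts. On that reading baseline weight is already in the primary test by subtraction. Only an additional covariate term is left open, and steps 2 and 4 show that term to be worth very little. This stands, and it is why the point is an improvement rather than a fault that threatens the trial.

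A reader might infer something stronger: that the primary test compares raw weights and so has 11% to 25% power, or that the 88% is wrong. The documents do not support either. Change is named as the outcome in three places, the 5 kg SD fits change and not weight, and the 88% reproduces. A reader might also infer that the conditional rule biases the result. It does not, because under randomization the adjusted and unadjusted comparisons target the same expected difference.

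The reply does not remove the rule itself. It is stated, it has no threshold or variable list, and it is the only guide to what the covariates in the primary test are. The sample size section also speaks of correlated weight measures over time, so repeated weights as the response cannot be excluded, and the test sentence does not settle how baseline would then enter.

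Fixing the covariates would not remove every data-dependent step. The choices of transformation, random effects and trajectory shape would remain.

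**Conclusion.** The point holds as a nearly free improvement. The primary model should not take its covariates from baseline significance tests when a better set is known in advance and already collected. On the change reading the gain from always including baseline weight is about 0 to 3 points of power, from 87.3% to between 87% and 90%. This rests on an SD of change of 5 kg, attrition of no more than 20%, and an assumed correlation of 0 to 0.3 in size. The further gain from the stratification factors was not quantified. The main benefit is that one primary analysis is fixed beforehand. The large power loss belongs only to a raw-weight comparison with no baseline term, which is a remote reading; stating how baseline enters rules it out.

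**What to change.** For the primary test, replace the conditional rule with a fixed covariate set of baseline weight, race/ethnicity and sex. State that the test is the between-arm difference in weight change from baseline to month 12, and name one model:

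- **Preferred:** weight at 0, 2, 6 and 12 months as response, baseline means constrained equal across arms, arm difference tested at month 12, stratification factors as covariates. This keeps all randomized participants. Baseline weight is part of the response here and should not also be a covariate.
- **Alternative:** change at months 2, 6 and 12 as response, with baseline weight, baseline-by-visit and the stratification factors as covariates. The small drawback is that participants with no post-baseline weight drop out.

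Adjustment for other baseline variables that turn out to be imbalanced becomes a sensitivity analysis.

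The cost is a few sentences of analysis text, with no new data, visits or participants. The change should be made before month-12 data are compared by arm. The document is dated December 2025 and does not say whether that has happened. If it has, report the fixed-covariate analysis alongside the existing one and label it as specified afterwards.
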